3.1.5 Definition of Maximum Tolerated Dose (MTD)

The primary objective is to estimate the MTD of external beam radiation that results in limiting acute toxicity. The MTD is defined as the dose level immediately below the dose level at which 2 or more in a cohort of either 3 or 6 patients experienced a DLT attributed to radiation therapy. If DLT does not occur at the highest dose level the protocol will be amended to escalate by 10% in cohorts of 3 patients each with the standard 3-6 dose escalation procedure.

3.2 PROTOCOL ADMINISTRATION

3.2.1 MR Imaging Guidelines

In all patients, conventional anatomic imaging (Fast spin echo T2 weighted scans) in the axial and coronal oblique planes will be obtained for research purposes to define the extent of the tumor. An endorectal coil may be indicated for prostate exams.

Following conventional anatomic imaging, one or more of the following research biological imaging tests will be performed. Examples include but are not exclusive to:

a) MR Spectroscopic Imaging (MRSI)

Using standard FDA approved spectroscopy software (General Electric Medical Systems, Milwaukee, WI); this will be performed using multiple voxels at multiple slices (“multivoxel-multislice MR spectroscopy”) which will generate a spectroscopic map of the area of interest reflecting the relative concentrations of various metabolites in the hydrogen resonance spectrum including citrate, choline, creatine, choline and lipids. This procedure may require approximately 30-45 minutes of scanning.

b) Dynamic Contrast Enhanced Magnetic Resonance Imaging (DCE-MRI)

This imaging study uses 1mmol/kg of an FDA approved Gadolinium chelate administered slowly by intravenous injection. Serial 3D dynamic enhanced MRI may be performed through the area of interest over a period of approximately 10 minutes. These data will be sent electronically to an independent workstation where a pixel by pixel time-signal intensity curve will be generated. This data will be automatically fit to a two compartment pharmacokinetic model using a custom designed image processing algorithm which will be used to generate semiquantitative parameters reflecting flow (“A”) and vessel permeability (k_{ep}). These parameters will be used to create color encoded maps which reflect the vascular flow and permeability of various regions.

c) BOLD

To accomplish this, the patient will first breathe room air via a regulated and non-magnetic tank set at 10L/min for 5 minutes via a specially designed breathing apparatus designed by [name]. of the Anesthesia Department. This breathing apparatus consists of a mouth piece and a clamp is place on the nose. It is non-invasive, and the patient can let go of the mouth piece if they find it uncomfortable.

Following this baseline study, the inhaled gas will be switched to regulated medical grade carbogen (5% carbon dioxide and 95% oxygen) in non-magnetic tanks administered at 10-15L/min for 7 minutes. This will improve the oxygenation of tissue by a combination of hyperoxia due to the high oxygen content and vasodilation due to carbon dioxide. Following carbogen inhalation the patient will be switched back to the room air at prior rates for 5 minutes. Images will be analyzed by measuring the difference in signal between the room air and carbogen scans and color maps reflecting per cent change in signal intensity will be generated for comparison.

d) OTHER Sequences

Other MRI sequences may be obtained. However, these other sequences will involve novel pulse sequences or post-processing of image data that will be transparent to the patient and will not require any additional procedures to be performed.

Of note, given the time required to perform and analyze these sequences as well as the length of the biopsy procedure, patients may have the target imaging with various high resolution sequences done at a separate time from the biopsy itself.

If the pelvic lymph nodes are visualized by MRI, then this information may be used to alter the nodal target volume.

3.2.2 *Tissue Collection*

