2.1.2 Exclusion Criteria

- 2.1.2.1 Cognitively impaired patients who cannot give informed consent.
- 2.1.2.2 Patients with metastatic disease beyond the pelvis.
- 2.1.2.3 Contraindication to biopsy:
 - Bleeding disorder

- PT/PTT \geq 1.5 times the upper limit of normal
- Platelets \leq 50K
- Artificial heart valve

2.1.2.4 Contraindication to MRI:

- Patients weighing >136 kgs (weight limit for the scanner tables)
- Allergy to MR contrast agent
- Patients with pacemakers, cerebral aneurysm clips, shrapnel injury or implantable electronic devices.

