8.3 MRI CONTRAST AGENT – Gadopentate dimeglumine

Manufacturer: Berlex Laboratories, Wayne NJ

Commercial name: Magnevist

Description: This is an FDA approved contrast agent in widespread use. Gadolinium produces MR contrast by altering the relaxivity of neighboring water protons. Experience at NIH has been obtained with over 30,000 intravenous injections.

Form: Gadopentate dimeglumine is available as Gd-DTPA. It is available as a sterile injectable liquid in single use ampules of 20 ml. The inactive ingredients are meglumine and diethylenetriamine pentaacetic acid.

Supply: Magnevist is commercially available and will be supplied by the Clinical Center Department of Radiology

Toxicities: The serious reaction rate (asthma, hives, seizures, hypotension) is less than 0.5%. The dose is 0.1 mmol/kg BW administered IV bolus via mechanical injector. There are no contraindications for its use. Gd-DTPA can be used in patients with elevated Cr. Levels and does not have known nephrotoxicity. Possible complications relate to extravasation of contrast in which localized swelling and pain may develop but because of the small volume (20cc) this does not lead to skin necrosis. There may be headache, nausea, vomiting, and transient sensations of heat or cold or taste disturbances following injection of gadopentetate.

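### Section 3.2.1(b) sets the DCE-MRI gadolinium dose at 1 mmol/kg, ten times the 0.1 mmol/kg in section 8.3, and is very probably a decimal error

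*Combined protocol and SAP*

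**What the plan says.** Section 3.2.1 (MR Imaging Guidelines) requires conventional anatomic imaging in all patients, after which "one or more of the following research biological imaging tests will be performed". Item (b) of that list is DCE-MRI, and its dosing instruction is "This imaging study uses 1mmol/kg of an FDA approved Gadolinium chelate administered slowly by intravenous injection". The item does not name the product.

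Section 8.3, headed "8.3 MRI CONTRAST AGENT – Gadopentate dimeglumine", is the only MRI contrast agent described in the document. Under toxicities it states "The dose is 0.1 mmol/kg BW administered IV bolus via mechanical injector". On presentation it says "It is available as a sterile injectable liquid in single use ampules of 20 ml". On extravasation it accepts that local swelling and pain may develop, but says that "because of the small volume (20cc) this does not lead to skin necrosis".

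No sentence gives DCE-MRI a separate, higher dose, and neither section refers to the other.

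**The concern.** The two sections prescribe different amounts of the same injected agent per kilogram. The higher figure is in the procedure section, which imaging staff would follow; the lower one sits in the toxicity paragraph of the pharmaceutical section.

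If 3.2.1(b) were followed as written, a patient would receive ten times the dose in 8.3. The safety statements in 8.3 would not carry over. The extravasation reassurance depends explicitly on a small volume, and the acceptance of patients with raised creatinine accompanies the 0.1 mmol/kg dose. The protocol would not catch the problem elsewhere: contrast allergy is an exclusion (2.1.2.4), but the listed laboratory tests (2.2.2 and 3.4.1) are PSA, PT/PTT and CBC, with no test of renal function.

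The sections also describe the injection differently, slow in one and a bolus by injector in the other. Neither gives a rate, so the size of that difference cannot be established.

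The statistical design is not at stake. DCE-MRI is one of several optional tests, and the discrepancy does not affect the MTD rule, the DLT definition, the sample size or the escalation probabilities. No harm to data comparability is claimed.

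**Working it through.** **Inputs from the document**
- Dose in 3.2.1(b): 1 mmol/kg.
- Dose in 8.3: 0.1 mmol/kg.
- Container in 8.3: 20 ml. Volume in the extravasation statement of 8.3: 20 cc.
- Heaviest eligible patient: 136 kg (exclusion 2.1.2.4).

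**Assumptions.** The document gives no concentration and no typical weight. I take weights of 50, 80 and 136 kg and concentrations from 0.25 to 1.0 mmol/mL.

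**Ratio.** 1 / 0.1 = 10.

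**Reproducing the 20 cc in 8.3.** Volume = dose per kg × weight / concentration. At 0.1 mmol/kg and 0.5 mmol/mL (mid-range), a 100 kg patient needs 0.1 × 100 / 0.5 = 20 mL and an 80 kg patient needs 0.1 × 80 / 0.5 = 16 mL. So 0.1 mmol/kg is consistent with about one ampule. At 1 mmol/kg and the same concentration, the volumes are 200 mL and 160 mL.

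**A check without a concentration.** Section 8.3 sets 0.1 mmol/kg beside a volume of about 20 cc. For the same product, ten times the dose is ten times the volume: 10 × 20 = 200 cc.

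**Concentration needed to fit each dose into 20 mL** (dose in mmol / 20):

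| Weight | Dose at 0.1 mmol/kg | Needed | Dose at 1 mmol/kg | Needed |
|---|---|---|---|---|
| 50 kg | 5.0 mmol | 0.25 mmol/mL | 50 mmol | 2.5 mmol/mL |
| 80 kg | 8.0 mmol | 0.40 mmol/mL | 80 mmol | 4.0 mmol/mL |
| 136 kg | 13.6 mmol | 0.68 mmol/mL | 136 mmol | 6.8 mmol/mL |

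**Volume over the assumed concentrations** (1.0 down to 0.25 mmol/mL):

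| Weight | At 0.1 mmol/kg | At 1 mmol/kg |
|---|---|---|
| 50 kg | 5 to 20 mL | 50 to 200 mL |
| 80 kg | 8 to 32 mL | 80 to 320 mL |
| 136 kg | 13.6 to 54.4 mL | 136 to 544 mL |

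At 0.1 mmol/kg the volumes run from 5 to 54.4 mL and include 20 mL. At 1 mmol/kg the smallest is 50 mL, which is 50 / 20 = 2.5 times the stated 20 cc. In 20 mL ampules, the 80 kg patient needs 8/20 to 32/20 = 0.4 to 1.6 at the lower dose and 80/20 to 320/20 = 4 to 16 at the higher.

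**The case against.** The strongest objection is that this is a clerical slip with no realistic route to harm. DCE-MRI is optional, and 3.2.1(b) names no product, so whoever prepares the injection has to consult 8.3, where the plausible dose is printed. Opening 4 to 16 ampules for one scan would stop most people. All of that is fair, and it makes literal execution unlikely. It does not justify leaving a tenfold error in a per-kilogram dosing instruction. It also leaves staff in an awkward position: under 7.3.8 any departure from the protocol is a deviation, and 7.4.1 requires every deviation to be reported, so even the evidently intended dose departs from 3.2.1(b).

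The inference from the 20 mL volume can also be challenged. The document states no concentration, an ampule does not cap a dose, and at 0.25 mmol/mL even 0.1 mmol/kg exceeds one ampule for an 80 kg patient (32 mL). The fit is therefore approximate. What survives is the pairing within 8.3: if about 20 cc goes with 0.1 mmol/kg, it cannot also go with ten times that dose of the same product. The conflict between the two stated doses does not need the inference at all; only the choice of which one is wrong does.

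A leading zero and decimal point might have been lost when the text was extracted from the PDF. The 0.1 in 8.3 survived, and nothing in 3.2.1(b) looks like a gap, but the possibility cannot be excluded without the source page.

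Finally, aligning the injection method and naming the product go beyond the decimal point. That is why both should depend on confirmation by the radiologist and pharmacist.

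**Conclusion.** The concern holds. Sections 3.2.1(b) and 8.3 give gadolinium doses that differ tenfold, with nothing to reconcile them, and 3.2.1(b) is very probably the one in error. For an assumed 80 kg patient the difference is 80 mmol against 8 mmol; at the 136 kg limit it is 136 against 13.6 mmol. The ratio needs no assumption. The volumes and ampule counts rest on the assumed weights and the 0.25 to 1.0 mmol/mL range. The judgement about which figure is wrong rests mainly on 8.3 placing 0.1 mmol/kg beside a 20 cc volume. Because this is an operative dosing instruction, it must be corrected even though it is unlikely to be carried out as written.

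**What to change.** First check the source page of 3.2.1(b) for a lost leading zero. If the page does read 1 mmol/kg, change the sentence to 0.1 mmol/kg of gadopentetate dimeglumine, given as an intravenous bolus by mechanical injector, with a cross-reference to 8.3. The responsible radiologist and pharmacist should confirm the dose and the injection method before the change is issued. If they want a slow injection for DCE-MRI, state the rate and make both sections agree.

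The cost is a one-line protocol correction, with no effect on design, sample size or analysis.

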3.2.2.1 General co-registration guidelines

Co-registration of the biopsy site to an MRI image will be accomplished by one of the following options: 1) real-time MR guidance of the biopsy procedure, 2) placing fiducial markers visible on MRI to identify sites selected for future biopsy, 3) fusing images from CT or Ultrasound-guided biopsy procedures to MR images, 4) repeat MRI immediately after a biopsy procedure to identify needle tracts.

Tissue will be collected with standard biopsy procedures (outlined below). NSAIDS should be discontinued one week prior to a biopsy procedure unless it is deemed unsafe or violates with the treatment protocol. Note that a separate consent specific to each pretreatment biopsy or fiducial marker placement procedure will be obtained.

3.2.2.2 Prostate biopsy

Needle biopsies will be performed in collaboration with surgeons from the Urologic Oncology Branch-NCI, and Radiologists from the Clinical Center-NIH. During each procedure, 2-10 samples will be obtained using 14-18 gauge tru-cut needles.

Biopsies will be performed according to standard techniques as follows. Patients undergo antibiotic prophylaxis with a quinolone antibiotic for one or two days before biopsy and the morning of biopsy. If the patient is known to be allergic to this antibiotic, or if they experience an allergic reaction to it, a different one, such as Bactrim will be prescribed. A rectal enema is self-administered. Patients void and then are placed in the prone position or in the left- or right-lateral decubitus position. A transrectal ultrasound or MRI probe (custom designed coil, approved by NMR Center Research Safety Subcommittee) is inserted and imaging measurements of the prostate obtained. After initial imaging is obtained, transperineal (or transrectal) introduction of 10-20 cc 1% lidocaine or 10cc of 0.25% bupivacaine is administered along the paraprostatic neurovascular bundle and the tip of the seminal vesicle. After 3 minutes of dwell time, transperineal (or transrectal), targeted prostate biopsy is performed as directed by imaging and 3-D spatialization (i.e. in the x,y,z coordinates). The patient recovers in the supine position and is allowed to ambulate shortly thereafter with a normal mean blood pressure. The patient is required to void without difficulty prior to discharge. Prostate biopsy is extremely well tolerated with complications occurring in 1% due mostly to infection, which can be treated in most cases with parenteral or enteral antibiotics as adjudged by the clinician.

3.2.2.3 Tissue Handling

[name] should be notified prior to specimen collection. Unless otherwise directed by [name], samples will be delivered to [name], [contact].

Samples will be divided at the time of the procedure. Half will be immediately fixed in formalin and submitted to the Laboratory of Pathology, NCI, for histopathological analysis. The remaining tissue will be placed in freezer vials and immediately frozen in liquid nitrogen.

3.2.2.4 Tissue Analysis

A diagnostic pathological evaluation will be performed on the specimens in collaboration with the laboratory of pathology – NCI. Supplementary tests, including but not exclusive to immunohistochemistry and counts of microvessel density, may be performed in a pilot exploratory fashion at the discretion of the principal investigator.

Tissue samples may then be processed for microarray testing. RNA will be isolated and pooled from the cell population of interest. Depending on the number of cells captured, amplification strategies may be explored.

Tissue specimens collected in the course of this research project may be banked and used in the future to investigate new scientific questions related to this study. However, this research may only be done if the risks of the new questions were covered in the consent document.

No germline mutation testing will be performed on any of the samples collected unless the patient gives separate informed consent. Tests will be pilot studies related to the Branch's work on such topics as molecular imaging, molecular profiling, and novel

molecular therapeutics. If any research tests are considered to be themselves of more than minimal risk to the patients, separate permission will be requested from the IRB to perform that test, and a new consent will be obtained.

At the completion of the protocol, the investigator will dispose of all specimens in accordance with the environmental protection laws, regulations and guidelines of the Federal Government and the State of Maryland.

All specimens obtained in the protocol are used as defined in the protocol. Any specimens that are remaining at the completion of the protocol will be stored in the conditions described below. The study will remain open so long as sample or data analysis continues. Samples from consenting subjects will be stored until they are no longer of scientific value or if a subject withdraws consent for their continued use, at which time they will be destroyed. The PI will report any loss or destruction of samples to the NCI IRB as soon as he is made aware of such loss.

If the patient withdraws consent the participants data will be excluded from future distributions, but data that have already been distributed for approved research use will not be able to be retrieved.

The PI will report destroyed samples to the IRB if samples become unsalvageable because of environmental factors (ex. broken freezer or lack of dry ice in a shipping container) or if a patient withdraws consent. Samples will also be reported as lost if they are lost in transit between facilities or misplaced by a researcher. Freezer problems, lost samples or other problems associated with samples will also be reported to the IRB, the NCI Clinical Director, and the office of the CCR, NCI.

3.2.3 Radiation Therapy

3.2.3.1 Prostate

3.2.3.1.1 Treatment planning

Planning target volume (PTV) 1 will be defined as the great vessels and a concentric 2.5 cm margin. Specifically, the aorta 2 cm proximal to the bifurcation, the common, internal, and external iliac vessels will be contoured. This margin may be edited at the treating physician's discretion (e.g. to meet normal tissue dose constraints). PTV 1 will be treated to a total dose of 4500 cGy in 180 cGy daily fractions in the first 10 patients. Thereafter, dose escalations will occur as per protocol. Daily dose will remain 180c Gy per day.

PTV 2 will be defined as the prostate and a 3 mm uniform margin. PTV 2 will be treated to a total dose of 75.6 Gy in 180 cGy daily fractions.

If indicated, the seminal vesicles may also be contoured and treated. When indicated, the seminal vesicles may be treated to 5400 cGy in 180 cGy.

3.2.3.1.2 Summary Of Dose Constraints:

Highest Priority:

- PTV2 will be defined as the prostate with a 3 mm uniform margin. The prescription dose to PTV2 will be 7560 cGy in 180 cGy daily fractions. No volume 4 mm beyond PTV2 will be allowed to receive a dose beyond 100% of the prescription dose.
- Less than 25% of the rectal volume will be irradiated to 70 Gy.
- The maximum dose to 10cc or more of small bowel will be no more than 5500 cGy.

Secondary Priority:

- PTV1 will be taken to full dose as per protocol.
- No more than 40% of the bladder will receive more than 6500 cGy.

3.2.3.2 Pelvic Lymph Nodes

see section 3.1

3.2.3.3 Radiation Treatment

Patients should begin their radiation treatment once pathology is available and at least 2 months of neoadjuvant hormone therapy has been completed. Patients will receive external beam radiation in the NCI Radiation Oncology Clinic daily, Monday – Friday except holidays.

3.4 ON-STUDY EVALUATION

3.4.1 Pre-Procedure (baseline)

- Informed consent obtained
- Clinical evaluation
 - History and physical exam
 - Vital signs
 - Pathology report confirming adenocarcinoma of the prostate
- EPIC
- AUA Symptom Score (Appendix IV)
- Sexual Health Inventory For Men (SHIM) (Appendix V)
- Laboratory evaluation
 - PSA
 - PT/PTT
 - CBC

3.4.2 Biopsy & Fiducial Marker Placement

- See Appendix III for MRI- Guided biopsy and FM data form
- Post fiducial marker placement MRI's may be performed to evaluate for marker migration
- No more than 12 biopsies will be performed.

3.4.3 Radiation Treatment Phase

- Weekly AP (or PA) and lateral port films
- The following acute rectal toxicity endpoints will be measured
 - RTOG acute toxicity grading- GI & GU (Appendix IIA) weekly and at the completion of treatment

3.4.4 Post Active Treatment Evaluation (follow- up)

- Upon completion of therapy, patients will be evaluated at 2, 4, 8 and 12 weeks for acute effects of radiation therapy. Patients will be evaluated at 6, 9, 12, 18 and every 6 months afterward for late effects until 36 months.
- Follow-up visits will include:
 - A directed history and physical examination,
 - PSA evaluation
 - Rectal toxicity assessment including:
 - RTOG acute toxicity grading- GI & GU (Appendix IIA)
 - RTOG Late toxicity grading- GI & GU (Appendix IIB)
 - EPIC (Appendix IIIC).
 - AUA Symptom Score (Appendix IV)
 - Sexual Health Inventory For Men (Appendix V)
- Follow-up MRI may be obtained after completion of therapy to better delineate the time of course of signal change after radiation therapy.

3.5 CONCURRENT THERAPIES

This study allows imaging and tissue procurement in high risk prostate cancer patients with risk of lymph node metastasis of at least 15% (as defined by 15% being included within the 90% confidence intervals of the Partin tables).

Such patients do require hormone therapy. Patients should receive at least neoadjuvant and concurrent hormone therapy. Higher risk patients may also receive indefinite adjuvant hormone therapy. Neoadjuvant hormone therapy usually consists of a non-steroidal anti-androgen (such as flutamide, an oral medication) and a gonadotropin releasing hormone agonist (such as leuprolide, an injectable medication). The non-steroidal anti-androgen is usually given for approximately 6-8 weeks. Concurrent and adjuvant hormone therapy usually consists of a gonadotropin releasing hormone agonist only.

3.6 SURGICAL GUIDELINES

None other than those required for standard biopsy procedures. Where clinically indicated, biopsies will be performed under appropriate analgesia, local/systemic anesthesia and/or conscious sedation with patient monitoring in compliance with hospital standards, no general anesthesia will be administered for research purposes only. Only biopsies that are “minimal risk” and do not require general anesthesia will be performed for research purposes only. Please refer to section 3.2.2. for details on the biopsy procedures.

3.7 RADIATION THERAPY GUIDELINES

Radiation Therapy is part of the primary protocol treatment and is therefore included in section 3.2.3

